## List of abbreviations

---

AE	Adverse Event
ALT	Alanine aminotransferase/glutamic pyruvic transaminase/GPT
AMI	Acute Myocardial Infarction
APC	Antigen Presenting Cell
AST	Aspartate aminotransferase/glutamic oxaloacetic transaminase/GOT
AUC	Area Under the Curve
BLRM	Bayesian Logistic Regression Model
CDP	Clinical Development Plan
██████████	██████████
CMO&PS	Chief Medical Office and Patient Safety
CRC	Colorectal cancer
CRF	Case Report/Record Form; the term CRF can be applied to either EDC or Paper
CRO	Contract Research Organization
CSR	Clinical study report
CSR addendum	An addendum to Clinical Study Report (CSR) that captures all the additional information that is not included in the CSR
CV	Cardiovascular
DCR	Disease Control Rate
DDP	Dose Determining Pharmacokinetic Set
DDS	Dose-Determining Safety Set
DLT	Dose Limiting Toxicity
DOR	Duration of Response
ECG	Electrocardiogram
ER	Estrogen Receptor
eSAE	Electronic Serious Adverse Event
EWOC	Escalation With Overdose Control
FAS	Full Analysis Set
FIH	First In Human
FU	Follow Up
GDPR	General Data Protection Regulation
GEJ	Gastro-Esophageal Junction
GLP	Good Laboratory Practice
HBV	Hepatitis B Virus
HCV	Hepatitis C Virus
HED	human equivalent dose
HER2	Human Epidermal growth factor Receptor 2
HNSTD	highest non-severely toxic dose
i.v.	Intravenous(ly)
IEC	Independent Ethics Committee
██████████	██████████
IG	Immunogenicity
██████████	██████████
IL-6	Interleukin-6
IRB	Institutional Review Board
irAE	Immune Related Adverse Event
irRC	immune related Response Criteria

---

[figure not shown]
ITIM	Immunoreceptor Tyrosine-based Inhibitory Motif
KO	Knockout
LAG-3	Lymphocyte activation gene-3
LLOQ	Lower Limit Of Quantitation
LMWH	Low Molecular Weight Heparin
mAb(s)	monoclonal Antibody(ies)
MHC	Major Histocompatibility Complex
MSI-H	Microsatellite instability high
MTD	Maximum Tolerated Dose
NOAEL	No Observed Adverse Effect Level
NPC	Nasopharyngeal cancer
NSCLC	Non-Small Cell Lung Carcinoma
NYHA	New York Heart Association
ORR	Overall Response Rate
█	█
PAS	Pharmacokinetic Analysis Set
PD	Pharmacodynamics
PD-1	Programmed Death-1
PD-L1	Programmed Death-Ligand 1
PD-L2	Programmed Death-Ligand 2
PFS	Progression Free Survival
PK	Pharmacokinetics
PPS	Per Protocol Set
PR	Progesterone Receptor
Q2W	Every 2 weeks dosing schedule
Q3W	Every 3 weeks dosing schedule
Q4W	Every 4 weeks dosing schedule
RAP	Report and Analysis Plan
RCC	Renal Cell Cancer
RECIST	Response Evaluation Criteria In Solid Tumors
RP2D	Recommended phase two dose
SAE	Serious Adverse Event
SEC	Safety Event Categories
SJS	Stevens-Johnson syndrome
TCR	T Cell Receptor
TEN	Lyell syndrome/toxic epidermal necrolysis
TIL(s)	Tumor Infiltrating Lymphocyte(s)
█	█
TNBC	Triple Negative Breast Cancer
TTR	Time To Response
US	United States
WT	Wild type

---

## Glossary of terms

Assessment	A procedure used to generate data required by the study
Biologic Sample	A biological specimen including, for example, blood (plasma, serum), saliva, tissue, urine, stool, etc. taken from a study subject or study patient
Cohort	A group of newly enrolled patients treated at a specific dose and regimen (i.e. treatment group) at the same time
Cycles	Number and timing or recommended repetitions of therapy are usually expressed as number of days (e.g.: q28 days)
Dose level	The dose of drug given to the patient (total daily or weekly etc.)
Enrollment	Point/time of patient entry into the study; the point at which informed consent must be obtained (i.e. prior to starting any of the procedures described in the protocol)
Investigational drug	The study treatment whose properties are being tested in the study; this definition is consistent with US CFR 21 Section 312.3 and is synonymous with “investigational new drug.”
Investigational treatment	Drug whose properties are being tested in the study as well as their associated placebo and active treatment controls (when applicable). This also includes approved drugs used outside of their indication/approved dosage, or that are tested in a fixed combination. Investigational treatment generally does not include other study treatments administered as concomitant background therapy required or allowed by the protocol when used in within approved indication/dosage
Patient Number (Patient No.)	A unique identifying number assigned to each patient/subject/healthy volunteer who enrolls in the study
Personal Data	Patient information collected by the Investigator that is transferred to Novartis for the purpose of the clinical trial. This data includes patient identifier information, study information, and biological samples.
Premature patient withdrawal	Point/time when the patient exits from the study prior to the planned completion of all study treatment administration and/or assessments; at this time all study treatment administration is discontinued and no further assessments are planned, unless the patient will be followed for progression [REDACTED]
Stage in cancer	The extent of a cancer in the body. Staging is usually based on the size of the tumor, whether lymph nodes contain cancer, and whether the cancer has spread from the original site to other parts of the body
Stop study participation	Point/time at which the patient came in for a final evaluation visit or when study treatment was discontinued whichever is later
Study treatment	Includes any drug or combination of drugs in any study arm administered to the patient (subject) as part of the required study procedures, including placebo and active drug run-ins.  In specific examples, it is important to judge investigational treatment component relationship relative to a study treatment combination; study treatment in this case refers to the investigational and non-investigational treatments in combination.
Study treatment discontinuation	Point/time when patient permanently stops taking study treatment for any reason; may or may not also be the point/time of premature patient withdrawal
Treatment group	A treatment group defines the dose and regimen or the combination, and may consist of 1 or more cohorts. Cohorts are not expanded, new cohorts are enrolled.
Variable	Identifier used in the data analysis; derived directly or indirectly from data collected using specified assessments at specified timepoints

Withdrawal of Study Consent	Withdrawal of consent from the study occurs only when a patient does not want to participate in the study any longer, and does not allow any further collection of personal data.
-----------------------------	---

**Protocol summary:**

Protocol number	CLAG525X2101C
Title	A Phase I/II, open label, multicenter study of the safety and efficacy of LAG525 single agent and in combination with PDR001 administered to patients with advanced malignancies.
Brief title	Phase I/II study of single agent LAG525 or combination of LAG525 and PDR001 in patients with advanced malignancies.
Sponsor and Clinical Phase	Novartis Phase I/II
Investigation type	Monoclonal antibody
Study type	Interventional
Purpose and rationale	
The purpose of this study is to characterize the safety, tolerability including determination of maximum tolerated dose (MTD) or recommended Phase 2 dose (RP2D), pharmacokinetics (PK), pharmacodynamics (PD) and anti-tumor activity of LAG525 as a single agent and in combination with PDR001, an antibody directed against PD-1 under investigation in a separate study ((PDR001X2101)).
 
In addition, the safety, tolerability, pharmacokinetics and pharmacodynamics of single-agent LAG525 in Japanese patients will be evaluated and characterized.
 
LAG-3 binds its ligand MHC Class II, and regulates T cell signaling. Blockade of LAG-3 has been shown to increase T cell proliferation and cytokine secretion, most notably IFN-<math>\gamma</math>. LAG-3 expression is also correlated with increased suppressive function in both FoxP3-positive natural regulatory T cells and induced FoxP3-negative regulatory cells.
 
By blocking the interaction between PD-1 and its ligands, PD-L1 and PD-L2, PDR001 inhibits the PD-1 immune checkpoint, resulting in activation of an antitumor immune response by activating effector T-cells and inhibiting regulatory T-cells.
 
Preclinical studies in the Sa1N fibrosarcoma and MC38 colon carcinoma models demonstrated tumor growth inhibition with anti-LAG-3 as a monotherapy with enhanced tumor growth inhibition observed with the combination of anti-LAG-3 and anti-PD-1 immunotherapy. Expression analysis in human tumor infiltrating lymphocytes (TILs) from cancer patients supports this conclusion, with LAG-3 and PD-1 co-expression identified on tolerized TILs in patients with ovarian cancer and microsatellite high colorectal carcinoma (MSI-H CRC).

Primary Objective(s)	
Phase I part
 
 
To estimate the RP2D or MTD for single agent LAG525 in all patients (including for Japanese patients)
 
To estimate the RP2D or MTD for the combination of LAG525 and PDR001
 
 
Phase II part
 
 
To estimate the overall response rate per RECIST V1.1 for single agent LAG525 as well as for the combination of LAG525 and PDR001
 

Secondary Objectives	

• To characterize the safety and tolerability of single agent LAG525 given alone and in combination with PDR001

• To characterize the pharmacokinetic profile of single agent LAG525 given alone and in combination with PDR001

• To assess emergence of anti-LAG525, and anti-PDR001 antibodies following one or more intravenous (i.v.) infusions of single-agent LAG525 given alone or in combination with PDR001

• To evaluate the preliminary antitumor activity of single agent LAG525 given alone or in combination with PDR001

Study design	
This study has been designed as a phase I/II, multi-center, open-label study starting with a phase I dose escalation part (including a separate Japanese single-agent dose escalation arm) followed by a phase II part.
 
Arm A: single agent LAG525 Arm B: combination of LAG525 and PDR001 Arm C: single agent LAG525 dose escalation in Japanese patients
 
Data from the dose-escalation arms will be analyzed separately and pooled as appropriate. If the recommended dose of single agent LAG525 is the same in Arms A and C, patients enrolled in Japan may be recruited into the Phase II single agent part of the study. In addition, if the recommended dose of PDR001 for Japanese patients in the PDR001X1101 study is the same as that determined in study PDR001X2101, Japanese patients may also enter the combination parts of study LAG525X2101 at whichever dose is being tested at that time.
 
Both PDR001 and LAG525 will be administered i.v. once every two weeks until a patient experiences unacceptable toxicity, progressive disease as per irRC or treatment is discontinued at the discretion of the investigator or the patient. In the combination cohort, the two antibodies will be administered separately with a break of 30 minutes between administrations. Infusions of each antibody can be extended to up to 2 hours if clinically indicated and the break between LAG525 and PDR001 antibody infusions can be up to 4 hours if clinically indicated. A cycle is defined as 28 days (21 days for patients on Q3W dosing schedule) for both monotherapy LAG525 and the combination of LAG525 and PDR001.
 
For the combination arm, the first dose for the first two patients treated at each untested dose level will be staggered by 24 hours.

Population	
The phase I part of the study will be conducted in adult patients with advanced solid tumors.
 
The phase II part of the study, both single agent and combination arms, will be conducted in adult patients with melanoma, NSCLC and renal cancer with or without PD-1/PD-L1 treatment experience. The combination arm will also be conducted in patients with mesothelioma and TNBC with or without PD-1/PD-L1 treatment experience.


Inclusion criteria
	
 
1. Written informed consent must be obtained prior to any procedures. For Japan only: written consent is necessary both from the patient and his/her legal representative if he/she is under the age of 20 years.
 
2. Age <math>\geq</math> 18 years
 
3. Phase I part: Patients with advanced/metastatic solid tumors, with measurable or non-measurable disease as determined by RECIST version 1.1 (refer to Appendix 1), who have progressed despite standard therapy or are intolerant of standard therapy, or for whom no standard therapy exists.
 
4. Phase II part: Patients with advanced/metastatic solid tumors, with at least one measurable lesion as determined by RECIST version 1.1, who have had disease progression. Additionally, the following must apply:             
 
a. NSCLC:                 
 
i. Disease recurrence or progression during or after no more than one prior platinum doublet-based chemotherapy regimen for advanced or metastatic disease. Prior maintenance therapy is allowed (considered pemetrexed, erlotinib, bevacizumab).
 
ii. Patients must have been tested for mutations affecting EGFR and/or ALK. (Patients with a known mutation in one gene need not be tested for the other). Patients with ALK or EGFR-positive NSCLC must have had recurrent or progressive disease after treatment with the corresponding inhibitor and no more than one platinum doublet-based chemotherapy, in any sequence.
 
 
 
b. Melanoma:                 
 
i. Patients with BRAF V600 mutation positive disease must have objective evidence of progression of disease after treatment with a BRAF inhibitor alone or in combination with other agents.
 
ii. Patients with BRAF wild-type disease must have objective evidence of progression of disease but are not required to have received prior therapy.
 
 
 
c. Renal:                 
 
i. Patients must have objective evidence of progression of disease during or following at least one regimen of treatment for advanced renal cancer.
 
 
 
d. Mesothelioma:                 
 
i. Patients must have objective evidence of progression of disease during or following at least one prior line of systemic chemotherapy for advanced disease.
 
 
 
e. TNBC:                 
 
i. Patients must have objective evidence of progression of disease during or following no more than 2 prior lines of systemic chemotherapy for advanced disease. Patients must have received a prior taxane-containing regimen.
 
 
 
 
 
5. ECOG Performance Status <math>\leq</math> 1.
 
6. Phase I Part: Patients enrolled in the Phase I part of the study must provide a new tumor biopsy at baseline and during treatment if medically feasible.
 
 
Phase II part: Patients enrolled in the Phase II part of the study must provide a new tumor biopsy at baseline and during treatment, if medically feasible.


Exclusion criteria (selected)
	
 
1. Presence of symptomatic central nervous system (CNS) metastases, or CNS metastases that require local CNS-directed therapy (such as radiotherapy or surgery), or increasing doses of corticosteroids within the prior 2 weeks. Patients with treated brain metastases should be neurologically stable for at least 4 weeks prior to study entry and off steroids for at least 2 weeks before administration of any study treatment.
 
2. History of severe hypersensitivity reactions to study treatment ingredients or other mAbs
 

	

3. Patient with out-of-range laboratory values defined as:

● Creatinine clearance (calculated using Cockcroft-Gault formula, or measured) < 40 mL/min

● Total bilirubin > 1.5 x ULN, except for patients with Gilbert's syndrome who are excluded if total bilirubin > 3.0 x ULN or direct bilirubin > 1.5 x ULN

● Alanine aminotransferase (ALT) > 3 x ULN

● Aspartate aminotransferase (AST) > 3 x ULN

● Absolute neutrophil count (ANC) < 1.0 x 10^9/L

● Platelet count < 75 x 10^9/L

● Hemoglobin (Hgb) < 9 g/dL

● Potassium, magnesium, calcium or phosphate abnormality CTCAE > grade 2

4. Clinically significant cardiac disease or impaired cardiac function

5. Active, known or suspected autoimmune disease. Patients with vitiligo, type I diabetes mellitus, residual hypothyroidism due to an autoimmune condition only requiring hormone replacement, psoriasis not requiring systemic treatment, or other conditions not expected to recur are permitted to enroll. Patients previously exposed to anti-PD-1 / PD-L1 treatment who are adequately treated for skin rash or who are receiving replacement therapy for endocrinopathies should not be excluded.

6. Patients who required discontinuation of treatment due to treatment-related toxicities with prior therapy directed against the same target as the drug(s) under study in this protocol.

7. History of drug-induced pneumonitis or current pneumonitis

8. Active infection requiring systemic antibiotic therapy. Patients requiring systemic antibiotics for infection must have completed therapy before screening is initiated.

9. HIV infection. Testing for HIV status is not necessary unless clinically indicated

10. Active hepatitis B virus (HBV) or hepatitis C virus (HCV) infection. Testing for HBV or HCV status is not necessary unless clinically indicated or the patient has a history of HBV or HCV infection.

11. Malignant disease, other than that being treated in this study

12. Any medical condition that would, in the investigator's judgment, prevent the patient's participation in the clinical study due to safety concerns, compliance with clinical study procedures or interpretation of study results.

13. a. Systemic anti-cancer therapy within 2 weeks of the first dose of study treatment. b. For cytotoxic agents that have major delayed toxicity, e.g. mitomycin C, nitrosoureas or more recent immunotherapies, 4 weeks is indicated as washout period. c. For patients receiving anticancer immunotherapies such as CTLA-4 antagonists, 8 weeks is indicated as the washout period.

14. Patients receiving chronic treatment with systemic steroid therapy (>10 mg/day prednisone or equivalent) within 7 days of the first dose of study treatment, other than replacement-dose steroids in the setting of adrenal insufficiency. Topical, inhaled, nasal and ophthalmic steroids are not prohibited.

15. Patients receiving systemic treatment with any immunosuppressive medication thought to interfere with the mechanism of action of the study drugs, other than replacement-dose corticosteroids in the setting of adrenal insufficiency.

16. Use of any live vaccines against infectious diseases within 4 weeks of initiation of study treatment.

17. Major surgery within 2 weeks of the first dose of study treatment.

--	--

	
18. Radiotherapy within 2 weeks of the first dose of study drug, except for palliative radiotherapy to a limited field, such as for the treatment of bone pain or a focally painful tumor mass. To allow evaluation of response to treatment, patients enrolled in the Phase II part must have remaining measurable disease that has not been irradiated.
 
19. Participation in an interventional, investigational study within 2 weeks prior to the first dose of study treatment.
 
20. Presence of <math>\geq</math> CTCAE grade 2 toxicity (except alopecia, peripheral neuropathy and ototoxicity, which are excluded if <math>\geq</math> CTCAE grade 3) due to prior cancer therapy.
 
21. Use of hematopoietic colony-stimulating growth factors (e.g. G-CSF, GM-CSF, M-CSF) <math>\leq</math> 2 weeks prior to the first dose of study treatment
 
22. Pregnant or lactating women, where pregnancy is defined as the state of a female after conception and until the termination of gestation, confirmed by a positive hCG laboratory test.
 
23. Women of child-bearing potential, defined as all women physiologically capable of becoming pregnant, unless they are using highly effective methods of contraception during dosing and for 150 days after the last dose of LAG525 or PDR001.
 
24. Sexually active males unless they use a condom during intercourse while taking the drug and for 150 days after stopping study treatment and should not father a child in this period. A condom is required to be used also by vasectomized men as well as during intercourse with a male partner in order to prevent delivery of the drug via seminal fluid.

Investigational and reference therapy	LAG525 and PDR001
Efficacy assessments	Tumor assessment per RECIST v1.1 and per irRC
Safety assessments	Incidence and severity of AEs and SAEs, including changes in laboratory values, vital signs and ECGs
Other assessments	Serum PK parameters and immunogenicity.
Data analysis	The study data will be analyzed and reported based on all patients' data of the Phase I and Phase II parts up to the time when all patients have completed at least six cycles of treatment or discontinued the treatment. Patient data from dose escalation will be analyzed by Arm and from Phase II by Group. Study data may be pooled where appropriate.
Key words	Phase I/II, LAG525, PDR001, Checkpoint inhibitor, PD-1, PD-L1, LAG-3.

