18. Radiotherapy within 2 weeks of the first dose of study drug, except for palliative radiotherapy to a limited field, such as for the treatment of bone pain or a focally painful tumor mass. To allow evaluation of response to treatment, patients enrolled in the Phase II part must have remaining measurable disease that has not been irradiated.
19. Participation in an interventional, investigational study within 2 weeks prior to the first dose of study treatment.
20. Presence of CTCAE  $\geq$  grade 2 toxicity (except alopecia, peripheral neuropathy and ototoxicity, which are excluded if  $\geq$  CTCAE grade 3) due to prior cancer therapy.
21. Use of hematopoietic colony-stimulating growth factors (e.g. G-CSF, GM-CSF, M-CSF)  $\leq$  2 weeks prior to the first dose of study treatment. Patients must have completed therapy at least 2 weeks prior to the first dose of study treatment with any hematopoietic colony-stimulating growth factors. An erythroid stimulating agent is allowed as long as it was initiated at least 2 weeks prior to the first dose of study treatment.
22. Pregnant or lactating women, where pregnancy is defined as the state of a female after conception and until the termination of gestation, confirmed by a positive hCG laboratory test.
23. Women of child-bearing potential, defined as all women physiologically capable of becoming pregnant, unless they are using highly effective methods of contraception during dosing and for 150 days after the last dose of LAG525 and/or PDR001. Highly effective contraception methods include:
  - Total abstinence (when this is in line with the preferred and usual lifestyle of the patient. Periodic abstinence (e.g., calendar, ovulation, symptothermal, post-ovulation methods) and withdrawal are not acceptable methods of contraception)
  - Female sterilization (have had surgical bilateral oophorectomy with or without hysterectomy), total hysterectomy or tubal ligation at least six weeks before taking study treatment. In case of oophorectomy alone, only when the reproductive status of the woman has been confirmed by follow up hormone level assessment
  - Male sterilization (at least 6 months prior to screening). For female patients on the study the vasectomized male partner should be the sole partner for that patient.

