## **7 Visit schedule and assessments**

### **7.1 Study flow and visit schedule**

Table 7-1 lists all of the assessments and indicates with an “X”, the visits when they are performed. All data obtained from these assessments must be supported in the patient’s source documentation. The table (“Category” column) indicates which assessments produce data to be entered into the clinical database (D) or remain in source documents only (S).

No CRF will be used as a source document.

Screening/baseline evaluations must be performed  $\leq 21$  days before Cycle 1 Day 1, except for baseline radiological evaluations which must be done within 28 days. Assessments required on Cycle 1 Day 1 that are performed as part of the screening evaluations and within 72 hours prior to the first dose of study treatment, do not need to be repeated on Cycle 1 Day 1. Laboratory and radiological assessments performed as part of standard of care prior to signing informed consent may be used if performed within the screening time window.

During the course of the study visits, test and/or procedures should occur on schedule whenever possible. A visit window of  $\pm 7$  days is allowed. If the infusion of LAG525 or its combination with PDR001 is delayed, the assessments will be shifted accordingly. On PK collection days the windows are provided in [Section 7.2.3](#).

Radiological assessments must be performed  $\pm 7$  days of the scheduled date of the assessment.

Visit name	Category	Protocol Section	Screening Phase	Treatment Phase												Follow-up				
			Screening	Cycle 1					Cycle 2		Cycle 3					Subsequent	EoT	Safety Follow-Up g	Disease Progression F/U	
Day of cycle			-21 to -1	1	2	8	11	15	1	15	1	2	8	11	15	1				
Urinalysis	D	7.2.2.5.4	X																	
Thyroid function	D	7.2.2.5.5	X	X					X		X					X	X			
Cytokines (IL-6)	D	7.2.2.5.6	X	In case of a suspected cytokine release syndrome																
Pregnancy test	D	7.2.2.5.7	X						X		X					X	X			
	S	7.2.2.5.7																X g		
Antineoplastic therapies since discontinuation of study treatment	D	7.1.5																X	X	X

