### 14.1.3 Definitions

#### 14.1.4 Disease measurability

In order to evaluate tumors throughout a study, definitions of measurability are required in order to classify lesions appropriately at baseline. In defining measurability, a distinction also needs to be made between nodal lesions (pathological lymph nodes) and non-nodal lesions.

**Measurable disease** - the presence of at least one measurable nodal or non-nodal lesion. If the measurable disease is restricted to a solitary lesion, its neoplastic nature should be confirmed by cytology/histology.

For patients without measurable disease see [Section 14.1.26](#).

**Measurable lesions** (both nodal and non-nodal)

- Measurable non-nodal - As a rule of thumb, the minimum size of a measurable non-nodal target lesion at baseline should be no less than double the slice thickness or 10mm whichever is greater - e.g. the minimum non-nodal lesion size for CT/MRI with 5mm cuts will be 10 mm, for 8 mm contiguous cuts the minimum size will be 16 mm.
- Lytic bone lesions or mixed lytic-blastic lesions with identifiable soft tissue components, that can be evaluated by CT/MRI, can be considered as measurable lesions, if the soft tissue component meets the definition of measurability.

- Measurable nodal lesions (i.e. lymph nodes) - Lymph nodes  $\geq 15$  mm in short axis can be considered for selection as target lesions. Lymph nodes measuring  $\geq 10$  mm and  $< 15$  mm are considered non-measurable. Lymph nodes smaller than 10 mm in short axis at baseline, regardless of the slice thickness, are normal and not considered indicative of disease.
- **Cystic lesions:**
  - Lesions that meet the criteria for radiographically defined simple cysts (i.e., spherical structure with a thin, non-irregular, non-nodular and non-enhancing wall, no septations, and low CT density [water-like] content) should not be considered as malignant lesions (neither measurable nor non-measurable) since they are, by definition, simple cysts.
  - ‘Cystic lesions’ thought to represent cystic metastases can be considered as measurable lesions, if they meet the definition of measurability described above. However, if noncystic lesions are present in the same patient, these are preferred for selection as target lesions.

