#### 14.1.7 Baseline documentation of target and non-target lesions

For the evaluation of lesions at baseline and throughout the study, the lesions are classified at baseline as either target or non-target lesions:

- **Target lesions:** All measurable lesions (nodal and non-nodal) up to a maximum of five lesions in total (and a maximum of two lesions per organ), representative of all involved organs should be identified as target lesions and recorded and measured at baseline. Target lesions should be selected on the basis of their size (lesions with the longest diameter) and their suitability for accurate repeated measurements (either by imaging techniques or clinically). Each target lesion must be uniquely and sequentially numbered on the CRF (even if it resides in the same organ).

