2.3.4 Prior antineoplastic therapy

Prior anti-neoplastic therapy will be summarized for medication, radiotherapy and surgery. The number (%) of patients who received any prior anti-neoplastic medication, radiotherapy or surgery will be summarized separately.

The summary of prior anti-neoplastic medications include the total number of regimens (note: there can be more than one medication per regimen), immuno-oncology therapeutic class, setting at last medication, best response at last medication (defined to be the best response during the last treatment regimens recorded) and time (in months) from start of last medication to progression. The last medication is defined based on the last start date of all prior regimen components. Prior antineoplastic medications is also summarized by Anatomical Therapeutic Chemical (ATC) class, and preferred term.

The summary of prior anti-neoplastic radiotherapy will include the radiotherapy locations, (including all locations recorded for each patient), setting at last radiotherapy and method.

The summary of prior anti-neoplastic surgery will include the time (in months) between the last surgery (non-biopsy procedure) to start of study treatment.

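### Lesions irradiated shortly before the first dose can be Phase II target lesions, so radiotherapy shrinkage can count towards the primary ORR

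*Protocol*

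**What the plan says.** **Eligibility.** Criterion 18 (Protocol summary and Section 5.3) excludes radiotherapy within 2 weeks of the first dose, "except for palliative radiotherapy to a limited field, such as for the treatment of bone pain or a focally painful tumor mass". For Phase II it adds that "patients enrolled in the Phase II part must have remaining measurable disease that has not been irradiated", and gives the evaluation of response as the reason.

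**Measurement.** Section 14.1.4 defines measurability by size: "the minimum size of a measurable non-nodal target lesion at baseline should be no less than double the slice thickness or 10mm", whichever is greater. It has special provisions for lytic bone lesions and cysts but none for irradiated lesions. Section 14.1.7 names as targets "All measurable lesions (nodal and non-nodal) up to a maximum of five lesions in total (and a maximum of two lesions per organ"). On the choice among lesions it says: "Target lesions should be selected on the basis of their size (lesions with the longest diameter) and their suitability for accurate repeated measurements". Irradiation is not a criterion. Table 14-1 reads PR on the sum over all targets against the baseline sum. Section 14.2.1 gives irRC the same baseline target definitions.

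**Timing.** Section 7.1 sets a 21-day screening window, "except for baseline radiological evaluations which must be done within 28 days".

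**Radiotherapy elsewhere in the plan.**
- Section 6.3.5 restricts on-study palliative radiotherapy to non-target lesions.
- The radiotherapy sensitivity analysis in Section 10.4.4 concerns on-treatment radiotherapy, and SAP 2.6.3 does not list it.
- SAP 2.7.1 exempts palliative radiotherapy from the rule that drops assessments made after other cancer therapy.
- The per-protocol set (SAP 2.2) requires a measurable lesion but does not ask whether it was irradiated.

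**The concern.** Criterion 18 recognises that irradiated disease is a poor basis for judging drug response. The measurement rules do not act on that. They guarantee that a non-irradiated lesion exists, not that response is read on it. A painful mass treated just before Cycle 1 Day 1 may be one of the patient's largest lesions, and size is one of the two stated grounds for choosing a target. If the baseline scan came before the radiotherapy, the whole radiotherapy effect falls after baseline.

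At stake are the primary ORR and the count that opens extension to 40 patients: 3 responses, or 2 in TNBC, under RECIST 1.1 or irRC. The endpoint is uncontrolled and investigator-assessed, in groups of 20 to 40, so no comparator arm would absorb the bias.

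**Working it through.** **1. When radiotherapy alone reaches PR.** Let w be the irradiated targets' share of the baseline sum and s their proportional shrinkage, with other targets unchanged. PR (Table 14-1) needs w × s ≥ 0.30, that is s ≥ 0.30/w:
- w = 0.5 needs 60% shrinkage, w = 0.6 needs 50%, w = 0.75 needs 40%.
- w below 0.30 cannot reach PR by radiotherapy alone.

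Example: targets of 60 mm (irradiated) and 30 mm (not irradiated). The first halves and the second is unchanged, so the sum goes from 90 to 60 mm. 30/90 = 33%, which meets the PR threshold.

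**2. Further conditions for a confirmed PR.** There must be no new lesion and no non-target progression (Table 14-3), and confirmation at least 4 weeks later (Section 7.2.1). The first scheduled scan is at about 8 weeks, so the patient must stay free of progression for roughly 12 weeks.

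**3. Reproducing the plan's false-positive rates** (Section 10.8, Tables 10-3 and 10-4). With true ORR p, extension at r1 of 20 and success at r of 40:

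P = Σ (x = r1 to 20) Bin(x; 20, p) × Pr[Bin(20, p) ≥ r − x]

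- NSCLC, renal, mesothelioma (r1 = 3, r = 12, p = 15%): 1.19%, stated 1.2%.
- TNBC (r1 = 2, r = 8, p = 10%): 4.12%, stated 4.1%.
- Melanoma (r1 = 3, r = 18, p = 30%): 3.20%, stated 3.2%.

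**4. Effect of radiotherapy-driven PRs.** Let c be the share of drug non-responders who become *confirmed* PRs through radiotherapy. The apparent ORR is p′ = p + (1 − p)c, which replaces p in the formula. At c = 4.5%, for example, p′ is 15% + 85% × 4.5% = 18.83%, 10% + 90% × 4.5% = 14.05%, and 30% + 70% × 4.5% = 33.15%.

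| c (assumed) | 12/40, true ORR 15% | TNBC 8/40, true ORR 10% | Melanoma 18/40, true ORR 30% |
|---|---|---|---|
| 0 | 1.2% | 4.1% | 3.2% |
| 0.2% | 1.3% | 4.5% | 3.3% |
| 1% | 1.8% | 6.3% | 4.0% |
| 2.25% | 2.9% | 9.9% | 5.2% |
| 4.5% | 6.0% | 18.9% | 7.9% |

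The values of c are products of two assumptions: the share of patients with an irradiated target, and the share of those who reach −30% by radiotherapy alone. They are 2% × 10% = 0.2%, 5% × 20% = 1% and 15% × 30% = 4.5%. The 2.25% row halves the last product, for the case where half of those patients progress elsewhere before confirmation.

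Expected extra responders per 20 patients are 20(1 − p)c: 0.14 to 0.18 at c = 1%, and 0.63 to 0.81 at c = 4.5%.

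**The case against.** The case for leaving the plan alone has five parts.

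- **An irradiated lesion need not be a target.** The five/two cap and suitability for repeated measurement also decide. The exemption's first example is bone pain. Blastic bone lesions are non-measurable, and lytic or mixed lesions count only with a measurable soft-tissue component. This stands: the lesion *can* be a target. A reader might infer that it always is one, and the text does not say so.
- **The intent is visible.** Criterion 18 ties response evaluation to non-irradiated disease, and Section 6.3.5 keeps on-study radiotherapy away from targets. This stands as intent, but neither passage governs the choice of targets at baseline.
- **Appendix 1 rests on the published RECIST 1.1 guideline.** That guideline is not among the documents, so silence in the appendix does not prove that the source is silent. However, Section 14.1.1 presents the appendix as the working rules needed for a consistent analysis, so the rule belongs there in any case.
- **The size is unknown and may be trivial.** This stands. No document gives the number of irradiated targets, and patients enrolled after progression may well progress elsewhere within 12 weeks. The c = 0.2% row barely moves the stated rates.
- **The error rates in Section 10.8 are conditional on a true ORR.** This stands too. A reader might infer that they assume every response is due to study drug, but the protocol makes no statement about attribution. The point is only that a biased measurement shifts the ORR that the design sees.

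**Conclusion.** The gap is real but narrow. Followed as written, the target rules can count shrinkage from radiotherapy given before the first dose as a confirmed response in the primary ORR, and no analysis in either document would show it. Confirmation at 4 weeks does not remove lasting shrinkage.

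The effect ranges from negligible to material. TNBC is the most exposed: it starts at 4.1% and is above the protocol's 5% mark at c = 1%. Melanoma passes that mark at c = 2.25%. The 12/40 groups pass it only at c = 4.5%. All of this rests on c, which is assumed, and on each irradiated responder being otherwise free of progression through confirmation. A reader might infer from the table that the trial's ORR was inflated by a known amount. The documents do not support that. They establish the route, not its frequency.

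**What to change.** 1. **SAP 2.6.3 (the main change).** Add a Phase II ORR sensitivity analysis that recalculates response after removing, at baseline and all visits, target lesions irradiated before the first dose. Where a radiotherapy site cannot be matched to a target, count that responder as a non-responder. List the responders who have an irradiated target.
2. **Protocol 14.1.7, and so 14.2, for any further enrolment.** State that in Phase II a lesion irradiated before the first dose, including after the baseline scan, is followed as non-target. Amendment 10 reports 235 patients already treated in the combination expansion, and targets are set at baseline, so this sentence alone would change little.

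**Cost.** No extra scans, and no change to eligibility or to the use of radiotherapy. Prior radiotherapy is recorded (Section 6.3.3), "The summary of prior anti-neoplastic radiotherapy will include the radiotherapy locations" (SAP 2.3.4), and lesion measurements are listed (SAP 2.7.2). Nothing in the documents links a radiotherapy field to a numbered target, so the matching needs case review. The result is a recalculated response beside the investigator-assessed primary one. Some patients will be left with fewer targets, but criterion 18 already requires each to have some non-irradiated measurable disease.
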